#### **9.6.4            Vital Signs**

The analyses of vital signs will include summary statistics for baseline, post-baseline values at all the time points, change from baseline to post-baseline values at all the time points, post-baseline maximum/minimum and change from baseline to post-baseline maximum/minimum by dose level for systolic blood pressure, diastolic blood pressure, heart rate and temperature.

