3.2.2.1 Toxicology

In the 1- and 3-month repeat-dose toxicology studies in the cynomolgus monkey (dose levels up to 300 and 100 μ g/kg, respectively, weekly subcutaneous [SC] injection), the no observed adverse effect level (NOAEL) dose was 30 μ g/kg based on the observation of increased heart rate with attenuated diurnal rhythm at 100 μ g/kg or greater. In addition, reversible decreases in red blood cell (RBC) mass, platelet and neutrophil counts were observed at 300 μ g/kg in the 1-month study. In the rat single-dose safety pharmacology study evaluating respiratory function (dose levels: 100, 500, and 2000 μ g/kg, single SC injection), audible respiration, decreased tidal volume and

increased respiration rate were observed at 2000 µg/kg. The heart rate, hematologic and respiratory changes were reversible, and are considered clinically monitorable.

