9.2.3.2 Vital Signs

The following measurements must be performed: Systolic/Diastolic Blood Pressure, Heart Rate, Respiratory Rate, and Temperature. Subject must be in a supine position in a rested and calm state for at least 5 minutes before blood pressure assessments are conducted. If the subject is unable to be in the supine position, the subject should be in most recumbent position as possible. The position selected for a subject should be the same that is used throughout the study and documented on the vital sign CRF. The temperature location selected for a subject should be the same that is used throughout the study and documented on the vital signs CRF. Record all measurements on the vital signs CRF.

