10.4.2.3.4 Vital Signs

The analyses of vital signs will include summary statistics at selected time points, post-baseline maximum/minimum and change from baseline to post-baseline maximum/minimum by dose level.

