**Immunogenicity data will be analyzed according to the actual treatment received.**

### **7. Planned Analyses**

#### **7.1 DLRMs**

DLRMs: The study will have DLRMs for each cohort after the last subject in the cohort completes the DLT evaluation period. Section [3.1](#) details the timing and scope of each DLRM planned for the study. All available data for subjects up to and including the data snapshot date will be included in the analysis based on an “as-is” snapshot of the database without data locking. Data will be subject to ongoing checks for integrity,

completeness and accuracy in accordance with the Data Management Plan; however, there is no requirement to resolve outstanding data issues ahead of the DLRM snapshot. DLRM analysis will include subject-level listings and plots of available safety data (labs, and vitals) for each cohort and the BLRM analysis if required. The recommendations for dose escalation/dose modifications will be based on the DLRMs.

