### **9.6.3            Laboratory Test Results**

#### **9.6.3.1        Chemistry and Hematology**

The analyses of safety laboratory endpoints will include summary statistics of baseline, post-baseline lab values at all the time points, change from baseline to post-baseline, post-baseline maximum/minimum and change from baseline to post-baseline maximum/minimum by dose level.

Shifts tables indicating the change between the baseline and the worst post dose CTCAE grades based on CTCAE version 4.03 or later will be provided for selected laboratory parameters of interest. Subject incidence of worst post-baseline eosinophils counts by the laboratory normal range will be provided.

**Chemistry and hematology laboratory tests performed by local laboratories will be included in the analyses where applicable in cases where central laboratory values were not obtainable (i.e. due to Covid restrictions).**

A listing of subjects identified as potential Hy's law cases (ALT or AST of >3xULN associated with total bilirubin > 2xULN and ALP <2xULN at a visit) will be provided with relevant laboratory tests included in the listing.

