#### **9.6.6            Electrocardiogram**

The ECG measurements will be performed as per standard of care for routine safety monitoring, rather than for purposes of assessment of potential QTc effect. Since these evaluations may not necessarily be performed under the rigorous conditions expected to lead to meaningful evaluation of QTc data; summaries and statistical analyses of ECG measurements are not planned, and these data would not be expected to be useful for meta-analysis with data from other trials.

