#### **10.            Changes From Protocol-specified Analyses**

The planned phase 1b interim analysis and phase 2 primary and final analyses are excluded from this analysis plan because the study is discontinued early. Instead, a final analysis will be conducted after the last subject in phase 1b part completes the study (including the treatment period and safety follow-up period).

---

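### SAP 9.6.4 leaves respiratory rate out of the final by-dose vital-sign summaries, although the protocol requires it to be measured

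*SAP*

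**What the plan says.** Protocol 9.2.3.2 lists the vital signs that must be taken as "Systolic/Diastolic Blood Pressure, Heart Rate, Respiratory Rate, and Temperature", and directs that all of them be recorded on the vital signs CRF. The protocol's analysis section (10.4.2.3.4) is general: "The analyses of vital signs will include summary statistics at selected time points, post-baseline maximum/minimum", plus change from baseline to those extremes, by dose level. It allows time points to be selected but neither names nor excludes any parameter.

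The SAP is more specific. Section 9.6.4 plans baseline values, post-baseline values at every time point, change from baseline, post-baseline extremes and change to those extremes, ending with "maximum/minimum by dose level for systolic blood pressure, diastolic blood pressure, heart rate and temperature". Respiratory rate is not in that list. SAP 9.6.1 counts vital signs as part of the primary safety analysis. SAP section 10, on departures from the protocol, addresses only the cancelled analyses: "The planned phase 1b interim analysis and phase 2 primary and final analyses are excluded from this analysis plan".

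On nonclinical safety, Protocol 3.2.2.1 describes faster respiration, among other respiratory findings, in a single-dose rat study at 2000 µg/kg. It concludes: "The heart rate, hematologic and respiratory changes were reversible, and are considered clinically monitorable".

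**The concern.** Of the five measurements the protocol makes mandatory, one disappears between data collection and the final tables, with no explanation. Where the sponsor decided not to tabulate another collected safety measure, it said so. SAP 9.6.6 states that "summaries and statistical analyses of ECG measurements are not planned" and gives the reason, as does Protocol 10.4.2.3.6.

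The missing parameter also belongs to one of the three groups of animal findings that Protocol 3.2.2.1 says can be monitored in the clinic. Heart rate is summarised under SAP 9.6.4, and hematology under SAP 9.6.3.1 ("summary statistics of baseline, post-baseline lab values at all the time points", with changes and extremes by dose level). The respiratory group has no corresponding summary of measured values.

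What is at stake is the completeness of the final safety description. A modest dose-related shift in respiratory rate that no investigator judged clinically significant would appear in no planned final summary, although the data would be in the database.

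**Working it through.** The plan gives no figure to reproduce, so the main check is a comparison of lists, followed by a count of the affected outputs and a look at how informative the missing table could be.

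**1. Measured against summarised**

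| Parameter | Must be measured (Protocol 9.2.3.2) | Final by-dose summary (SAP 9.6.4) |
|---|---|---|
| Systolic blood pressure | yes | yes |
| Diastolic blood pressure | yes | yes |
| Heart rate | yes | yes |
| Temperature | yes | yes |
| Respiratory rate | yes | no |

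Five are measured and four summarised. SAP sections 7 to 10, 13 and Appendix G contain no reason for the difference and no separate respiratory-rate summary. SAP 9.6.4 shows no sign of redaction.

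**2. Outputs affected**

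The vitals table in SAP Appendix G already defines the analysis windows. Counting post-baseline windows:

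- Week 1: 5 (days 2, 3, 4, 8, 11)
- Weeks 2 to 14: 13
- Week 15: 1
- Week 16: 4 (day 113 pre-dose, days 114, 115, 116)
- Weeks 17, 18 and 20: 3
- Subtotal: 5 + 13 + 1 + 4 + 3 = 26
- Weeks 22 to 52 in steps of 2: (52 − 22)/2 + 1 = 16, so 26 + 16 = **42 through week 52**
- Weeks 22 to 258 in steps of 2: (258 − 22)/2 + 1 = 119, and week 260 adds 1, so 26 + 119 + 1 = **146 through week 260**

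As written, none of these windows would carry a respiratory-rate summary, and no post-baseline maximum or minimum would be produced. These are defined windows, not expected data. The study was terminated early, and only responding subjects with sponsor agreement continue past week 52. The 42 windows through week 52 are therefore the more relevant figure.

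**3. Precision of the missing summary**

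Cohorts are planned at 3 to 6 DLT-evaluable subjects (Protocol 5.1.1). For a mean change at one time point, the 95% confidence interval half-width in standard deviation (SD) units is t(0.975, n − 1)/√n:

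- n = 6: 2.571/2.449 = **1.05 SD**
- n = 3: 4.303/1.732 = **2.48 SD**

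The documents give no SD for respiratory rate, so these cannot be converted to breaths per minute. The calculation assumes approximately normal changes and no missing values. The same half-widths in SD units apply to the four vital signs that are summarised.

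**The case against.** The strongest reply is that no explicit commitment is broken and little is lost. Protocol 10.4.2.3.4 names no parameters, and choosing what to tabulate is ordinary SAP work. SAP 9.6.5, for instance, reduces physical measurements to weight. It is therefore arguable whether SAP section 10 had to record the choice. The ECG comparison is also loose, because it concerns a whole assessment rather than one parameter.

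The animal signal is limited: a single-dose rat study, the top dose only, and reversible. The NOAEL was set on heart rate in monkeys, and heart rate is summarised. Calling a change monitorable concerns monitoring, which the protocol provides by measuring respiratory rate.

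Other routes exist too. SAP 9.6.2 names tachypnea as a possible event of interest. Protocol Appendix 4 makes clinically significant vital-sign abnormalities adverse events. For dose level review meetings, SAP 7.1 says "DLRM analysis will include subject-level listings and plots of available safety data (labs, and vitals) for each cohort", and Protocol Appendix 3 adds that safety data collected after the DLT period are included. Small changes would in any case be hard to attribute in an uncontrolled trial that admits subjects with lung cGVHD.

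Most of this stands as a limit on the weight of the point. It does not fill the gap:

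- The review-meeting outputs are interim, taken from an unlocked database, and do not name which vital signs are shown.
- The adverse-event route captures only what an investigator judges clinically significant and not due to progression of the underlying disease.
- SAP 9.1 limits the study report to critical subject-level listings, so a respiratory-rate listing is not assured.
- Imprecision and difficulty of attribution apply equally to the four parameters that are kept, so they do not explain dropping the fifth.

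**Conclusion.** The concern holds and is minor. Followed as written, the SAP would omit measured respiratory rate from the final by-dose safety summaries, although collection is mandatory and the protocol's own toxicology section makes the parameter relevant. The effect is confined to descriptive safety reporting: one of five vital signs, across up to 42 defined windows through week 52. Sample size, DLT evaluation, the Bayesian dose-escalation model and every other stated in-study decision are unaffected. The conclusion rests on reading the four parameters named in SAP 9.6.4 as the complete specification. The verb used there (include) is not strictly exclusive, but a programmer would build the tables from that list.

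**What to change.** Add respiratory rate to the parameters in SAP 9.6.4, with the same outputs as the other vital signs: values at each time point, change from baseline, post-baseline maximum and minimum, and change to those extremes, all by dose level. Stating a reason for the omission would tidy the documentation but would still leave the measurements out of the final analysis, so adding the parameter is the better course.

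The cost is negligible: one phrase in the SAP and one more parameter in an existing table program. The data are already recorded on the vital signs CRF, and the Appendix G vitals windows can be used unchanged. The resulting table should be read as descriptive, given the cohort sizes.

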#### **9.6.5            Physical Measurements**

The analyses will include summary statistics of weight at scheduled time-points and by dose level.

#### **9.6.6            Electrocardiogram**

The ECG measurements will be performed as per standard of care for routine safety monitoring, rather than for purposes of assessment of potential QTc effect. Since these evaluations may not necessarily be performed under the rigorous conditions expected to lead to meaningful evaluation of QTc data; summaries and statistical analyses of ECG measurements are not planned, and these data would not be expected to be useful for meta-analysis with data from other trials.

#### **9.6.7            Antibody Formation**

If needed, exploratory analyses of the relationship between safety and immunogenicity may be performed.

#### **9.6.8            Exposure to Investigational Product**

The number of days on IP and the total dose of IP will be summarized using descriptive statistics. Number and percentage of subjects who missed IP doses due to COVID-19 measures will be summarized. The final IPD list will be used to identify such subjects.

A listing of the unique manufacturing lot numbers, and a listing of the subjects administered each manufacturing lot number will be provided

### **9.6.9            Exposure to Concomitant Medication**

Number and proportion of subjects receiving medications/therapies of interest will be summarized by preferred term or category as coded by the World Health Organization Drug (WHODRUG) dictionary.

**Number and proportion of subjects who experienced a systemic corticosteroid dose reduction from baseline in subjects who were on systemic corticosteroid at baseline will be summarized by treatment group through week 52.**

### **9.7            Other Analyses**

#### **9.7.1            Analyses of Pharmacokinetic or Pharmacokinetic/Pharmacodynamic Endpoints**

##### **9.7.1.1        Analysis of Pharmacokinetic Endpoint**

Pharmacokinetics analyses will be performed by Clinical Pharmacology, Modeling and Simulation (CPMS) group. The Pharmacokinetic Concentration Analysis set defined in Section 6.3.1 will be used in analyzing PK endpoints. Serum concentrations of efavaleukin alfa will be expressed in ng/mL. All concentrations below the limit of quantification or missing data will be labeled as such in the concentration data listings. Concentrations below the lower limit of quantification will be treated as zero in summary statistics.

Actual dosing and sampling times and nominal doses (unless subjects had dosing errors, dosing changes, or dosing interruptions) will be used for individual concentration-time plots and calculation of PK parameters for each subject. The reasons for excluding any sample from the analyses will be provided.

Individual concentration-time data will be tabulated and presented graphically. Summary of PK concentration over time and PK parameters will be provided. Mean concentration-time profiles for each dose will be provided. PK observations with missing concentration, missing dose, missing elapsed time will be excluded from PK statistical summary. PK parameters will be summarized for each dose using descriptive statistics, including subject numbers, mean, standard deviation, CV, median and range.

##### **9.7.1.2        Analysis of Pharmacodynamic Endpoints**

The Pharmacodynamic (PD) Analysis set defined in Section 6.3.3 will be used.

**PD assessments include but are not limited to:**

[REDACTED]

[REDACTED]

[figure not shown]
[REDACTED] Due to the skewed distribution of PD data, mean, standard deviation and standard error will be estimated based on log-transformed data, and the estimates will be back-transformed and presented, which are equivalent to geometric mean, geometric standard deviation and geometric standard error.

To maintain the integrity of PD results, data collected at an end of treatment or end of extended treatment visit which is completed outside the upper limit of protocol defined window (> 9 days after the last dose date for QW cohorts and > 16 days for Q2W cohorts) will not be included in the analysis. In addition, data collected at a visit after skipping one or more consecutive doses prior to that visit will be also excluded from analysis (the same window will be used as above i.e. (> 9 days after the last dose date for QW cohorts and > 16 days for Q2W cohorts).

#### **9.7.1.3 PK/PD Analysis**

Pharmacokinetic/pharmacodynamic modeling may be performed to explore relationship between efavaleukin alfa exposure and PD efficacy/safety endpoints by CPMS.

#### **9.7.2 Analyses of Clinical Outcome Assessments**

#### **9.7.3            Analyses of Biomarker Endpoints**

Not Applicable

#### **10.            Changes From Protocol-specified Analyses**

The planned phase 1b interim analysis and phase 2 primary and final analyses are excluded from this analysis plan because the study is discontinued early. Instead, a final analysis will be conducted after the last subject in phase 1b part completes the study (including the treatment period and safety follow-up period).

---

**12. Prioritization of Analyses**

There is no prioritization of analyses.

**13. Data Not Covered by This Plan**

Exploratory data not included in this plan may be analyzed at a later date or may be analyzed by a different Amgen Department.

---

**14. Appendices**

## Appendix A. Technical Detail and Supplemental Information Regarding Statistical Procedures and Programs

### Imputation Rules for Partial or Missing Start Dates

The reference date for the following rules is the date of first dose of IP.

Start Date		Stop Date						Missing	
		Complete: yyyymmdd		Partial: yyyymm		Partial: yyyy			
		< 1 st dose	≥ 1 st dose	< 1 st dose yyyym m	≥ 1 st dose yyyym m	< 1 st dose yyyy	≥ 1 st dose yyyy		
Partial: yyyymm	= 1 st dose yyyymm	2	1	n/a	1	n/a	1	1	
	≠ 1 st dose yyyymm		2	2	2	2	2	2	
Partial: yyyy	= 1 st dose yyyy	3	1	3	1	n/a	1	1	
	≠ 1 st dose yyyy		3		3	3	3	3	
Missing		4	1	4	1	4	1	1	

1=Impute the date of first dose;

2=Impute the first of the month;

3=Impute January 1 of the year;

4=Impute January 1 of the stop year;

Note: For subjects who were never treated (first dose date is missing), partial start dates will be set to the first day of the partial month or first day of year if month is also missing.

### Imputation Rules for Partial or Missing Stop Dates

Initial imputation

- If the month and year are present, impute the last day of that month.
- If only the year is present, impute December 31 of that year.
- If the stop date is entirely missing, assume the event or medication is ongoing.

If the imputed stop date is before the start date, set stop date to missing.

---

If the imputed stop date is after the death date, impute as death date.

### **Imputation Rules for Partial or Missing Death Dates**

If death year and month are available but day is missing:

- If yyyyymm for the date last known to be alive equals yyyyymm for death date, set death date to the day after the date last known to be alive.
- If yyyyymm for the date last known to be alive is less than the yyyyymm for death date, set death date to the first day of the death month.
- If yyyyymm for the date last known to be alive is greater than yyyyymm for death date, assume date last known to be alive is in error, set death date to the first day of the death month.

If month and day are missing and year of death is known:

- If yyyy for the date last known to be alive equals yyyy for death date, set death date to the day after last known to be alive date.
- If yyyy for the date last known to be alive is less than yyyy for death date, set death date to the first day of the death year.
- If yyyy for the date last known to be alive is greater than yyyy for death date, assume date last known to be alive is in error, set death date to the first day of the death year.

If a death date is totally missing:

- Set death date to the day after the date last known to be alive. If the date last known to be alive is a partial date, set it to the first day of the month last known to be alive or first day of the year last known to be alive if month is also missing.

---

### **Appendix B. Reference Values/Toxicity Grades**

The Common Terminology Criteria for Adverse Events (CTCAE) version 4.03 will be used and is available at the following location

[Common Terminology Criteria for Adverse Events \(CTCAE\) | Protocol Development | CTEP \(cancer.gov\)](#)

### Appendix C. Bayesian Logistic Regression Model

[figure not shown]
The study will use BLRM to guide dose escalation. The MTD target toxicity probability interval for DLT is (0.20, 0.30), and TPIs of (0.30, 0.60) and (0.60, 1.00) are defined as excessive and unacceptable, respectively. The design seeks to identify a dose most likely to have a DLT rate in the target TPI, but with overdose control that limits the possibility the dose has an excessive or unacceptable DLT rate (Babb et al, 1998).

Let  $\mathbf{d}=(d_1, \dots, d_k)$  denote the vector of all efavaleukin alfa doses to be studied in the study. The probability of a DLT at dose level  $d_i, i=1, \dots, k$  is assumed to follow a Bernoulli distribution with probability  $p_i$  where the logit of  $p_i$  increases linearly with the log of the standardized dose in the following 2-parameter logistic model:

$$\log\left[\frac{p_i}{1-p_i}\right] = \text{logit}(p_i) = \log[a] + \exp(\log[b]) \log\left(\frac{d_i}{\max(\mathbf{d})}\right)$$

where a and b are random variables and  $d_i$  is dose level represented by predicted

[REDACTED]).  $d_k$  is an additional dose assuming Treg concentration = [REDACTED] that's higher than the currently planned doses. Thus  $\mathbf{d} = [REDACTED]$ . If additional dose cohorts were added during study conduct (e.g., decision following a DLRM), the value of  $\mathbf{d}$  will be updated.

A minimally informative prior distribution (Neuenschwander et al, 2008) was selected for  $\theta = (\log[a], \log[b])$ , where the probability that the true DLT rate is  $\leq 0.20$  at the lowest dose is 0.90 and the probability the true DLT rate is  $\leq 0.50$  at the maximum dose is 0.90. Median values for  $p_i$  were interpolated per the logistic model. For each  $d_i$ , 2 quantiles for  $p_i$  were selected from a minimum informative Beta distribution with the target median. This set of quantiles fully specified a target prior for theta. A bivariate normal distribution for  $\theta$  was assumed where  $(\log[a])$  has a normal distribution with mean ma and standard deviation sa, and  $(\log[b])$  has a normal distribution with mean mb and standard deviation

sb, and r is the correlation between  $\log[a]$  and  $\log[b]$ . Numerical integration with the R “integrate” function was used to calculate  $\Pr[p_i \leq q(d_i)]$  where  $q(d_i)$  is a quantile for dose  $d_i$ . An optimal bivariate normal distribution was estimated that achieved the minimum sum of squared difference between achieved and specified quantiles across all doses using a non-linear optimization with the R “optim” function. The bivariate normal distribution prior solution has  $ma = -1.283$ ,  $sa = 1.002$ ,  $mb = 0.280$ ,  $sb = 0.770$ , and  $r = -0.568$ .

The operating characteristics of the BLRM model were evaluated via simulation with cohort size of 3. All simulated studies started with an initial dose strength of [REDACTED] and subsequent doses were selected based on the following rules:

- After each cohort, the next dose is the one with the highest probability of the target TPI, but with a less than 0.25 probability of an excessive or unacceptable TPI.
- If  $\geq 1$  subject has a DLT at a dose, then no higher dose can be evaluated unless there are at least 6 evaluable subjects at this lower dose.

No skipping of planned dose is allowed.

The dose escalation will be stopped given one or more of the following conditions:

- The model recommends the same dose  $> 3$  times (not necessarily sequentially)
- A maximum of 24 subjects is evaluated.

The design was evaluated for three possible dose-response scenarios consistent with the design’s model: “Low”, “Mid”, and “High” MTD. The possible dosing strength in the simulation is [REDACTED], where [REDACTED] and [REDACTED] was added to simulate the “High MTD” scenario where the true MTD exceeds the currently planned dose. See [Table 2](#) for the probability profiles of the three scenarios (acceptable MTDs (between 0.2 to 0.3) are marked bold)

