5.4 Justification for Investigational Product Dose

Based on data from Study 20160283 as of 27 October 2020, efavaleukin alfa has demonstrated acceptable safety and tolerability in patients with cGVHD at doses up to [REDACTED] µg Q2W administered for up to 54 weeks. Efavaleukin alfa has also demonstrated pharmacodynamic selectivity with greater fold increase in the mean blood Treg counts compared to mean CD4 Tcon counts across all the doses and dosing frequencies tested although high inter-subject variability in response was observed. The increases in CD4+ Tcon were minimal and demonstrated both inter-subject and inter-visit variability. The observed safety profile and pharmacodynamics of efavaleukin alfa in cGVHD patients support further dose escalation to investigate whether higher Treg expansion can be achieved with continued maintenance of selectivity.

The additional efavaleukin alfa dose of [REDACTED] µg Q2W was selected based on about 2-fold higher predicted drug exposures than the [REDACTED] µg Q2W dose with about 9-fold and 1.3-fold exposure margins of AUC and C_{max} relative to the NOAEL dose in the 3-month toxicology study. The observed exposures of efavaleukin alfa in cGVHD patients are approximately dose proportional. The proposed dose of [REDACTED] µg Q2W was selected to minimize overlap in exposures compared to the observed exposures at the [REDACTED] µg Q2W dose (Table 3-1). The cohort 5 dose of [REDACTED] µg Q2W is predicted to have good separation in exposure based on the estimated interquartile ranges (IQRs) of AUC and C_{max} at the [REDACTED] µg Q2W dose.

Population PK/PD modeling was performed to predict efavaleukin alfa Treg expansion in humans following [REDACTED] and [REDACTED] µg doses given QW and [REDACTED] and [REDACTED] µg doses given Q2W. Exposure response relationships were modelled using observed efavaleukin alfa human exposures and pharmacodynamic outputs from cohorts 1 through 8 ([REDACTED] to [REDACTED] µg) of the SAD, FIH study in healthy subjects and all available PK/PD data from 3 phase 1b studies: 20170103 (up to [REDACTED] µg Q2W in subjects with SLE); 20170149 (up to [REDACTED] µg Q2W in subject with RA); and this study, 20160283 (up to [REDACTED] µg Q2W). For each dosing frequency (QW or Q2W), predicted [REDACTED]
[REDACTED]

consistent with observed data. The [REDACTED] µg Q2W dose is predicted to produce a roughly 30% increase in the [REDACTED] compared to the [REDACTED] µg Q2W dose.

6. Study Population

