The probability of each TPI and of a DLT will be summarized by dose along with the estimated dose-toxicity curve. A final estimate of the MTD will be estimated from the Bayesian model by utilizing all DLT-evaluable subjects. Please refer to [Appendix C](#) for more details on the BLRM and its operation characteristics. Before each DLRM, the above BLRM will be fitted with the prior distribution as specified in [Appendix C](#). This model will only be used to aid DLRM dosing decision thus the recommendation of the model is non-binding in nature.

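### The BLRM's reference dose is max(d), which can change if a dose above d_k is added, while the printed prior is tied to one value of max(d): a minor gap that matters for the final MTD estimate

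*SAP*

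**What the plan says.** - **Model.** SAP 9.6.2.1 and Appendix C use a two-parameter logistic model in which the logit of the DLT probability "increases linearly with the log of the standardized dose in the following 2-parameter logistic model". The standardised dose is d_i / max(d), and the intercept is log(a).
- **Contents of d.** Doses enter on a predicted scale that is redacted. The vector already includes a last element d_k, set at a value "that's higher than the currently planned doses".
- **Updating d.** Appendix C: "If additional dose cohorts were added during study conduct (e.g., decision following a DLRM), the value of" d will be updated. Section 9.6.2.1 repeats this. Neither place says what then happens to the reference dose or to the prior.
- **Prior.** It is calibrated so that a DLT rate of at most 0.20 has probability 0.90 at the lowest dose, and a DLT rate of at most 0.50 has the same probability at the maximum ("at the maximum dose is 0.90"). One result is printed: "The bivariate normal distribution prior solution has" ma = -1.283, sa = 1.002, mb = 0.280, sb = 0.770 and r = -0.568.
- **Use.** Before each dose level review meeting (DLRM), "the above BLRM will be fitted with the prior distribution as specified in" Appendix C. The model is used once at least one DLT has been seen. It recommends the dose most likely to lie in the target interval, subject to a probability below 25% in the excessive and unacceptable intervals, that is, above a DLT rate of 0.30. Section 9.6.2.1 calls the recommendation non-binding, but still plans a final MTD estimate from all DLT-evaluable subjects.

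**The concern.** In this parameterisation log(a) is the log-odds of DLT at whatever dose is currently max(d). Its prior was fitted for one particular max(d). If max(d) grows and the prior numbers stay as printed, the belief held about the old top dose is transferred to the new top dose, and every existing dose slides down the same curve.

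A recommendation or an MTD estimate could then change because the dose vector was relabelled, not because subjects were observed. Two analysts with the same DLT data, one using the calibration value of max(d) and one using a larger updated value, could report different MTDs. The effect is largest near the top of the dose range, where overdose control matters most.

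**Working it through.** **Inputs.** The five prior values and the model come from SAP Appendix C. The overdose cut-off of 0.25 for a DLT rate above 0.30 comes from SAP 3.1, 9.6.2.1 and Appendix C. The dose values are redacted, so k = new max(d) / old max(d) and all dose fractions below are assumptions.

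**1. Reproduce the plan's own figure.** At d = max(d) the slope term is zero, so Pr(p ≤ 0.50) = Pr(log a ≤ 0) = Φ(1.283/1.002) = 0.900. This matches the stated 0.90 and confirms that the printed prior is anchored at max(d). The lowest-dose figure cannot be checked directly. The prior gives 0.90 there if the lowest dose is about 0.12 of max(d).

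**2. Effect of a larger max(d).** For fixed a and b, with b = exp(log b) > 0:

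logit p = log a + b·log(d_i / (k·max(d))) = [log a + b·log(d_i / max(d))] − b·log k.

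For k > 1 every existing dose loses b·log k on the logit scale, so its prior DLT probability falls. If the added dose is at or below d_k, then k = 1 and nothing changes.

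**3. Prior at the old maximum** (numerical integration over the stated bivariate normal):

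| k | Pr(p ≤ 0.50) | Pr(p > 0.30) | Median DLT rate |
|---|---|---|---|
| 1 | 0.900 | 0.332 | 0.217 |
| 1.25 | 0.927 | 0.248 | 0.165 |
| 1.5 | 0.942 | 0.202 | 0.132 |
| 2 | 0.957 | 0.152 | 0.093 |

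**4. Which doses can cross 0.25.** Only the ratio d_i / (k·max(d)) matters. The k = 1.25 row is therefore also the k = 1 result for a dose at 1/1.25 = 0.8 of the old maximum, which is 0.248. Under the prior, any dose at or below about 0.8 of the old maximum already meets the limit and cannot cross it. At half the old maximum, k = 2 moves Pr(p > 0.30) from 0.152 to 0.086, both well under 0.25.

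**5. After data.** The model is run only after a DLT, so posteriors are what count.

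- One DLT in 4 subjects at the old maximum: Pr(p > 0.30) there is 0.30, 0.25 (0.247), 0.22 and 0.19 for k = 1, 1.25, 1.5 and 2.
- 0/6, 0/6, 1/6 and 2/6 DLTs at 0.125, 0.25, 0.5 and 1 of the old maximum: Pr(p > 0.30) at the top dose is about 0.30, 0.17 and 0.12 for k = 1, 1.5 and 2. The posterior mean at the lowest dose goes the other way: 0.027, 0.033 and 0.037.
- All 63 data sets with 0 to 3 DLTs in 6 subjects at each of three doses and at least one DLT (4³ − 1 = 63), for two dose layouts and k = 1.5 and 2: the posterior mean fell at the highest dose given in 63 of 63, at the middle dose in 57 of 63, and at the lowest dose in only 13 to 22 of 63. The largest rise at any dose was 0.025. The 0.25 limit at the highest dose given was crossed in 6 (k = 1.5) or 10 (k = 2) of 63 when that dose was the old maximum, and in none when it was half of it.

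**6. With a fixed reference.** Holding the denominator at its calibration value keeps k = 1 for existing doses: Pr(p > 0.30) at the old maximum stays 0.332 whatever is added.

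**The case against.** The best defence is the buffer dose. Because d_k sits above the planned doses, adding a cohort at or below it leaves max(d) and every fit unchanged. This stands, and it limits the point to additions above d_k.

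A reader might infer that cohort 5 has already caused the problem, since Protocol 5.4 introduces it as an addition ("The additional efavaleukin alfa dose of", value redacted). The documents do not support that. The SAP counts cohort 5 among the five planned levels, and on its own wording d_k lies above those. Nothing unredacted shows that cohort 5 raised max(d).

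A reader might also infer that all doses already given come to look safer. That is exact for the prior but not for the posteriors the plan would use, where the lowest dose often rises slightly. Crossings of the 0.25 limit arise mainly for doses close to the old maximum, and that maximum, d_k, is not itself a planned cohort.

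That the prior stays fixed is an inference. It rests on the sentence in 9.6.2.1 and the single printed solution, and Appendix C also describes a calibration procedure that could be rerun. Rerunning it would not cure the problem: placing the 0.90 anchor at the new maximum would again move the old maximum below it.

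Finally, the practical stakes are small. The model is non-binding, enrolment to cohort 5 at its planned dose was stopped, the study was terminated early, and the SAP's primary objective no longer mentions estimating the MTD. All of this stands and bears on weight. It does not remove the ambiguity in the final estimate.

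**Conclusion.** The point holds as a minor one. The SAP ties the prior to max(d), allows d to be updated, and neither fixes the reference dose nor recalibrates the prior. If an added dose exceeds d_k, the prior DLT probability of every existing dose falls without new data. In every data set tried, the posterior mean at the highest dose given fell as well.

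The actual size cannot be given because d is redacted. For an assumed 1.25-fold rise, prior Pr(p > 0.30) at the old maximum goes from about 0.33 to 0.25; for assumed 1.5- and 2-fold rises it goes to about 0.20 and 0.15. The documents do not show that any of this occurred. What remains open is which max(d) the final MTD estimate in SAP 9.6.2.1 would use, if a DLT was observed and d was updated.

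**What to change.** In SAP 9.6.2.1 and Appendix C, replace max(d) in the model by a fixed reference dose d*, equal to the value used to calibrate the printed prior. Add one sentence: d* stays the same in all fits, including the final one, when d is updated; a dose above d* simply has d_i/d* greater than 1.

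The cost is one symbol and one sentence. It needs no new data or simulation, leaves the printed prior as it is, and changes no dose or clinical rule.
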